1.3.2 Part 1B – Preliminary Food Effect Assessment

Part 1B (the preliminary food effect assessment) will be assessed by a predefined schedule in [Table 2](#) from Day -7 until Day 3. The fasting window is defined in Part 1B as 10 hours predose to 4 hours postdose. For assessments after Day 4 see Part 1A Schedule of Activities ([Table 1](#)).

Note: After M4076 PK is established, the minimum required time interval (washout) between the first 2 administrations of M4076 may be adjusted (minimum of 5 times the half-life of M4076, but at least 1 day and not > 6 days). Additionally, if the half-life of M4076 is substantially longer than originally predicted, an additional PK time point on Day -5 may be added and earlier time point(s) removed so that the total number of blood draws is not increased.

Table 2 Schedule of Activities: Preliminary Food Effect Assessment, Part 1B

Assessment and Procedures	Screen	Food Effect Assessment									Treatment	Notes
Day	D-28 to -8	-7	-6	-5	-4	-3 to -1	1	2	3	4		
Visit Window (days)							-1					Day 1 assessments that could be completed on Day -1 are limited to physical examination, height/weight, and ECOG performance status.
Study Site Visits	X	X	X	X	X	Wash out days	X	X	X	See Table 1		After Day 4 participants will continue to be treated as per Table 1 (Schedule of Activities for Part 1A).
Written informed consent	X											
Inclusion/Exclusion Criteria	X											
Medical history (includes substance usage); Demography	X											Substances: tobacco use only.

Assessment and Procedures	Screen	Food Effect Assessment								Treatment	Notes
Day	D-28 to -8	-7	-6	-5	-4	-3 to -1	1	2	3	4	
Visit Window (days)							-1				Day 1 assessments that could be completed on Day -1 are limited to physical examination, height/weight, and ECOG performance status.
Hepatitis B and C tests	X										To rule out active infection, performed at the Investigator's discretion.
Optional HIV Screening	X										HIV testing is optional at the Investigator's discretion.
Pregnancy Test (WOCBP only)	X	X					X				Serum test at Screening, urine test otherwise. Urine pregnancy results must be available prior to M4076 dosing.
ECOG performance status	X	X					X				See Appendix 10 .
Safety Assessments											
Physical Examination	X						X				Refer to Section 8.2.1 .
Height and Weight	X						X				Collect height at screening only.
Imaging Disease Assessment (CT/MRI)	X										
Vital Signs	X	X					X				Vital signs are to be measured as follows: 
Day -7 and Day 1, at predose (within approximately 30 to 60 minutes prior) and

Assessment and Procedures	Screen	Food Effect Assessment									Treatment	Notes
Day	D-28 to -8	-7	-6	-5	-4	-3 to -1	1	2	3	4		
Visit Window (days)							-1					Day 1 assessments that could be completed on Day -1 are limited to physical examination, height/weight, and ECOG performance status.
												• 4 hours (\pm 1 hour) postdose
Serum Chemistry	X	X					X					See Appendix 6 for details.
Hematology and Coagulation (PT, aPTT, INR)	X	X					X					See Appendix 6 for details.
Urinalysis	X	X					X					See Appendix 6 for details.
Standard 12-lead ECG	X											
TriPLICATE digital ECG		X					X					ECG should only be collected for participants dosed in the fasted state. See Table 4 for triPLICATE ECG details.
AE and SAE assessment	Continuous											
Concomitant medications and procedures review												

Assessment and Procedures	Screen	Food Effect Assessment								Treatment	Notes
Day	D-28 to -8	-7	-6	-5	-4	-3 to -1	1	2	3	4	
Visit Window (days)							-1				Day 1 assessments that could be completed on Day -1 are limited to physical examination, height/weight, and ECOG performance status.
Study Intervention and Treatment											
Low-fat Meal or Overnight Fasting (Fasting window: 10 hours predose to 4 hours postdose)		X	X				X				Participants in Part 1B will be randomly assigned on a 1:1 basis to 1 of 2 study intervention sequences: (1) fasted followed by fed, or (2) fed followed by fasted. After completion of food effect assessments, participants may continue to receive study intervention at RDE from D4 onward (on an empty stomach) and follow assessments as per Table 1 from D8 onwards.
M4076 Administration (single dose)		X					X			X	After D4, M4076 dosing should continue at the RDE and thereafter follow assessments as per Table 1 .
Pharmacokinetic Assessments:											
Blood – PK blood samples M4076		X	X	X	X		X	X	X	X	See Table 4 for PK sample details.
Urine PK Collection		X	X	X	X		X	X	X	X	See Table 4 for urine PK sample details.
CCI											

Assessment and Procedures	Screen	Food Effect Assessment								Treatment	Notes
Day	D-28 to -8	-7	-6	-5	-4	-3 to -1	1	2	3	4	
Visit Window (days)							-1				Day 1 assessments that could be completed on Day -1 are limited to physical examination, height/weight, and ECOG performance status.
CCI											
Plasma – Circulating Tumor DNA Sample		X									Collect predose.
Fresh Paired Tumor Biopsies	X									X	Mandatory collection, if not contraindicated for medical reasons. The first of two paired biopsies must be collected anytime during screening. The second biopsy must be collected on D4 from 2 to 4 hours after study intervention. No bone biopsies are allowed.
Blood - Immune Phenotyping		X									Collect predose.
Serum/plasma – Circulating Factors		X									Collect predose.

AE = adverse event; aPTT = activated partial thromboplastin time; CT = computed tomography; D = Day; DNA = deoxyribonucleic acid; ECG = electrocardiogram; ECOG = Eastern Cooperative Oncology Group; HIV = human immunodeficiency virus; INR = international normalized ratio; MRI = magnetic resonance imaging; Pd = pharmacodynamic; PK = pharmacokinetic; PT = prothrombin time; RDE = recommended dose for expansion; SAE = serious adverse event; WOCBP = woman of childbearing potential.

1.3.3

Parts 1A and 1B – Pharmacokinetic, ECG, and Schedule

CCI

ampling

Table 3

Part 1A M4076 Monotherapy Dose Escalation: Pharmacokinetic, ECG and Assessments

CCI

Study Day	M4076 Dosing	PK Sampling Time	ECG ^b	Paired Biopsies	CCI
Screening (D -28 to -1)				X	
Day 1	X	Predose ^a	X		
		0.5 hour ± 10 minutes postdose			
		1 hour ± 10 minutes postdose			
		2 hours ± 10 minutes postdose	X		
		3 hours ± 20 minutes postdose	X		
		4 hours ± 20 minutes postdose	X		
		6 hours ± 20 minutes postdose	X		
Day 2	X	Predose ^a	X		
		2 hours -4 hours postdose ^c		X ^c	
Day 8	X	Predose ^a	X		
		1 hour ± 10 minutes postdose	X		
		2 hours ± 10 minutes postdose	X		
		3 hours ± 20 minutes postdose	X		

Study Day	M4076 Dosing	PK Sampling Time	ECG ^b	Paired Biopsies	CCl [REDACTED]
		4 hours ± 20 minutes postdose	X		
		6 hours ± 20 minutes postdose			
		8 hours ± 20 minutes postdose	X		
Day 9	X	Predose ^a			
Day 22	X	Predose ^a			X
		2 hours ± 10 minutes postdose			X
		4 hours ± 20 minutes postdose			X
All subsequent Day 1 of every 3 week treatment period	X	Predose ^a			

Note: The fasting window in Part 1A is defined as: 2 hours predose to 1-hour postdose in general, and 2 hours predose to 4 hours postdose on days where PK-time matched triplicate ECG will be collected.

ECG = electrocardiogram; γ-H2AX = gamma histone family member X; CCl [REDACTED]; PK = pharmacokinetic.

^a All predose samples have a window of -60 minutes prior to dosing.

^b The window period for ECG is the same as noted for PK sampling.

^c Efforts should be made to collect blood for PK and CCl [REDACTED] and biopsy samples around similar time points (± 20 minutes).

Cl

Period 1 Day 8/9 PK sampling may be conducted on Day 15/16, or Period 2 Day 1/2, if required for logistical reasons and/or in case study intervention was interrupted and resumed. In this case, timing of associated triplicate ECG measurements should be rescheduled accordingly, and the Sponsor notified in advance.

Table 4

Part 1B Preliminary Food Effect Assessment: Pharmacokinetic, ECG and CCI Assessments

Study Day	M4076 Dosing	PK Sampling Time	Urine Collection for PK	ECG ^b	Paired Biopsies	CCI
Screening (D -28 to -8)					X	
-7	X	Predose ^a	X (1 hour, 0)	X		
		0.5 hour ± 10 minutes postdose	X (0 to 4 hours)			
		1 hour ± 10 minutes postdose		X		
		2 hours ± 10 minutes postdose		X		
		3 hours ± 20 minutes postdose		X		
		4 hours ± 20 minutes postdose	X (4 to 8 hours)	X		
		6 hours ± 20 minutes postdose		X		
		8 hours ± 20 minutes postdose	X (8 to 24 hours)	X		
		10 hours ± 20 minutes postdose				
-6		24 hours ± 2 hours postdose	X (24 to 48 hours)			
-5		48 hours ± 2 hours postdose	X (48 to 72 hours)			
-4		72 hours ± 2 hours postdose				
Day -3 to -1 Washout						

Study Day	M4076 Dosing	PK Sampling Time	Urine Collection for PK	ECG ^b	Paired Biopsies	CCI
Day 1	X	Predose ^a		X		
		0.5 hour ± 10 minutes postdose	X (0 to 4 hours)			
		1 hour ± 10 minutes postdose				
		2 hours ± 10 minutes postdose		X		
		3 hours ± 20 minutes postdose		X		
		4 hours ± 20 minutes postdose	X (4 to 8 hours)	X		
		6 hours ± 20 minutes postdose		X		
		8 hours ± 20 minutes postdose	X (8 to 24 hours)	X		
		10 hours ± 20 minutes postdose				
Day 2		24 hours ± 2 hours postdose	X (24 to 48 hours)			
Day 3		48 hours ± 2 hours postdose	X (48 to 72 hours)			
Day 4 ^d	X	Predose ^a				
		1 hours ± 10 minutes postdose				
		3 hours ± 60 minutes postdose			X ^c	
		6 hours ± 20 minutes postdose				
		8 hours ± 20 minutes postdose				

ECG = electrocardiogram; γ-H2AX = gamma histone family member X; Pd = pharmacodynamic; PK = pharmacokinetic; RDE = recommended dose for evaluation.

^a All predose samples have a window of – 60 minutes prior to next dosing.

- d** Triplicate ECG collection is only applicable to participants dosed in the fasted state. The fasting window in Part 1B is defined as 10 hours predose to 4 hours postdose.
- c** The biopsy can be collected anytime between 2 and 4 hours after treatment administration. Efforts should be made to collect PK ad Pd blood and biopsy samples around similar time points (\pm 20 minutes).
- d** After completion of Part 1B assessments, participants may continue to receive study intervention at RDE from D4 onward (on an empty stomach) and follow assessments as per [Table 3](#) from D8 onwards.

2 Introduction

M4076 (MSC2585823A) is a potent, selective and orally bioavailable adenosine triphosphate competitive inhibitor of ataxia-telangiectasia mutated (ATM) kinase. ATM plays a central role in the deoxyribonucleic acid (DNA) damage response and ATM inhibitors enhance the cytotoxic effects of DNA damaging therapies such as radiotherapy and DNA double-strand break (DSB)-inducing chemotherapies. M4076 also has monotherapy antitumor activities in a subset of cancer cell models.

Detailed information on the chemistry, pharmacology, efficacy, and safety of M4076 is in the M4076 Investigator's Brochure (IB).

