Overall Design: This is an open-label, Phase 1, clinical study of M4076. Part 1A is a M4076 monotherapy dose escalation designed to determine the safety, tolerability, PK, pharmacodynamics and early signs of efficacy in participants with solid tumors. Once an RDE is declared in Part 1A, a preliminary food effect cohort, Part 1B, may follow and will be conducted at the RDE or a lower dose than RDE determined from Part 1A. Part 1B is a randomized, 2-sequence, 2-period, cross-over design.

Disclosure Statement: This is an unblinded sequential treatment study with 2 parts: dose escalation (Part 1A) and food effect study (Part 1B).

Number of Arms: Not applicable.

Blinding: No blinding

Number of Participants: Approximately 40 participants are planned to be assigned to study intervention, including 22 to 28 participants in Part 1A (planned 4 potential dose levels) and 12 participants in Part 1B; the sample size for the MTD and/or RDE dose level needs to be at least 6 participants.

Study Intervention Groups and Duration: It is estimated that participants will be on the study for an approximate duration of 105 days/15 weeks.

[figure not shown]
Involvement of Special Committee(s): Safety Monitoring Committee.

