4.1.1 Part 1A – M4076 Monotherapy Dose Escalation

Part 1A of the study will define the MTD and/or RDE of M4076 monotherapy in participants with advanced solid tumors for which no standard therapy is available.

The first dose escalation cohort of 3 participants will receive M4076 monotherapy at the starting dose of 100 mg administered orally once daily under fasting conditions (see Section 6.1 for fasting window information). For further dose escalation cohorts, an SMC will meet and review all available safety, PK and Pd data to provide recommendations on the DL for the next cohort. A Bayesian dose-toxicity model (Appendix 12) will assist the SMC in dose recommendations. For details of statistical considerations, see Section 9.

Potential DLs are: 100 mg (starting dose), 200 mg, 300 mg, 400 mg, 600 mg. A DL of 50 mg will be explored in case the starting dose of 100 mg is not tolerated. Depending on the observed toxicity profile and available PK and Pd, the SMC may decide on doses different to, or higher or lower from what is prespecified. The SMC may also recommend changing the dosing regimen to e.g. thrice weekly (daily dosing on Days 1, 3, and 5 of each week), twice weekly (daily dosing on Days 1 and 4 of each week), and/or schedules with holidays from study intervention (e.g., 3 days on/4 days off, 7 days on/14 days off, 14 days on/7 days off). More details on the SMC and dose escalation can be found in Section 6.6.1. The SMC operational details will be provided in an SMC Charter, which will be established prior to the start of recruitment. The details will include, but not limited to SMC membership, meeting frequencies, minimum requirements for data review, and responsibilities.

Dose escalation will proceed according to SMC recommendation until MTD and/or a safe RDE is determined and/or the SMC recommends ending dose escalation. The MTD and RDE are defined by the SMC. Target DLT probability for the MTD determination is 30%. In determining the RDE, the SMC will also consider PK, Pd and information on the safety and tolerability of the study intervention beyond the DLT period.

At least 6 participants are required to be treated at the MTD and/or RDE.

RDE cannot exceed MTD. If suggested RDE is below MTD, dose escalation will continue until MTD is reached (if applicable) or SMC decides ending dose escalation.

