At the discretion of the SMC, if the toxicity and tolerability profile of M4076 remains ambiguous at any DL, including the MTD or if additional PK/Pd data are felt necessary at any DL below the MTD, additional participants may be studied at that DL to better define the toxicity, tolerability, PK, and Pd. The study procedures for these additional participant(s)/cohort(s) will be the same as that specified for other study participants/cohorts.

This study part will also investigate the pharmacodynamics of M4076 as a secondary objective. Paired tumor biopsies (optional) and serial blood samples (mandatory) will be collected to evaluate markers of ATM inhibition.

If necessary, the Schedule of Activities will be adjusted, e.g. to ensure that PK and Pd samples are collected at the appropriate time points.

Once the MTD and/or RDE is determined in Part 1A, the RDE from Part 1A will be used for the food effect cohort in Part 1B.

Intraparticipant Dose Escalation: No intraparticipant dose escalation is allowed. However, upon declaration of safety and tolerability of the MTD or RDE by the SMC, participants who are still receiving ongoing study intervention at doses lower than the RDE may be switched to the RDE if participants have not experienced any treatment-emergent related AEs greater than Grade 1.

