Part 1B (the preliminary food effect assessment) will be conducted with two single doses of M4076 of the same amount. The dose of M4076 to be administered is planned to be the RDE, although a lower dose may be used at the discretion of the SMC. Based on nonclinical data and predicted high degree of absorption that is expected to be dose-linear up to 600 mg, a clinically relevant food effect is not anticipated. Based on nonclinical repeat dose toxicity and pharmacokinetic studies of M4076, increased exposure as a result of coadministration with food for a single dose is not expected to substantially alter the risk.

See Section 6.6 for information on dose selection and modifications.

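### SAP Sections 9 and 14 give opposite answers on which over-dosed participants count in the efficacy summaries; a minor, conditional gap concerns the Day 4 dose if Part 1B runs below the RDE

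*Protocol*

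**What the plan says.** **Over-dosed participants (SAP).**

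- SAP Section 9 sets the actual dose from compliance over the first 21 days, relative to the planned level on the eCRF Cohort page. In Table 1, a participant above 100% of plan who reaches at least 80% of a higher level is assigned to that level. The note under Table 1 removes from the Pd and efficacy summaries only a participant above 120% of plan who is also at or below 80% of the next higher level.
- SAP Section 14 removes everyone above 120% of plan from the efficacy summaries. It has no second condition and no window.
- On the dose used for efficacy, the SAP disagrees with itself. The FAS/SAF definition in Section 8.1 and the actual-dose text in Section 9 point to actual dose. The note closing Section 8.1 puts everything other than safety, PK and Pd by planned dose.

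**Part 1B dose (Protocol).**

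- Sections 1.1 and 4.1 say that Part 1B "will be conducted at the RDE or a lower dose than RDE determined from Part 1A". Section 4.2 says the dose is "planned to be the RDE, although a lower dose may be used at the discretion of the SMC".
- For later dosing, the Part 1B schedule names only the RDE. The Table 2 administration note says "After D4, M4076 dosing should continue at the RDE". The Table 2 meal note says "After completion of food effect assessments, participants may continue to receive study intervention at RDE from D4 onward", and Table 4 footnote d likewise says "participants may continue to receive study intervention at RDE from D4 onward".
- The only rule on raising a participant's dose is in Section 4.1.1, under the Part 1A heading. It bans such increases, except that participants below the RDE "may be switched to the RDE if participants have not experienced any treatment-emergent related AEs greater than Grade 1". Section 4.1.2, on Part 1B, neither repeats nor cites it.

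**The concern.** Two rules in one SAP select different participants for the same tables. A programmer following Section 9 would show an over-dosed participant in a higher dose column; one following Section 14 would show no such participant. The usual cohort is 3 participants, so one person is a third of a column for ORR or PFS.

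The missing window in Section 14 adds to this. SAP Section 13 defines cumulative dose as the overall total. If Section 14 is read that way, it can reach participants who were never over-dosed and were moved up to the RDE as Protocol 4.1.1 allows. Those who stay longest after the switch would be the likeliest to cross 120%, so the exclusion would be related to outcome.

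The Part 1B point is separate. If the SMC uses the lower-dose option, a site following Table 2 would raise the dose on Day 4 without being told whether the Grade 1 condition applies. The scheduled Part 1B SMC review comes when the sixth participant has been treated for 28 days (Protocol 9.4.4), by which time the first six would normally be past Day 4.

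**Working it through.** The plan states no figure on this point to reproduce. The check compares thresholds.

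**Inputs.** Protocol 4.1.1: "Potential DLs are: 100 mg (starting dose), 200 mg, 300 mg, 400 mg, 600 mg", with 50 mg as fallback. SAP Section 9: limits of 120% and 80%. SAP Section 14: limit of 120%.

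**Step 1: where the rules disagree.** Expressed as a share of plan, 80% of the next level is 0.8 × next / planned.

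| Planned (mg) | Next (mg) | 0.8 × next / planned | Section 9 note drops | Section 14 drops | Opposite results |
|---|---|---|---|---|---|
| 100 | 200 | 160% | above 120%, up to 160% | above 120% | above 160% |
| 200 | 300 | 120% | no one | above 120% | above 120% |
| 300 | 400 | 106.7% | no one | above 120% | above 120% |
| 400 | 600 | 120% | no one | above 120% | above 120% |
| 600 | none | – | not defined | above 120% | not defined |
| 200, if no 300 mg level | 400 | 160% | above 120%, up to 160% | above 120% | above 160% |

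The 50 mg fallback behaves like 100 mg (0.8 × 100 / 50 = 160%). The last row matters because Protocol Appendix 12 lists no 300 mg level, whereas 4.1.1 does.

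**Step 2: one example.** A plan of 200 mg daily for 21 days is 4,200 mg. Suppose 5,400 mg is taken. That is 5,400 / 4,200 = 128.6% of plan and 5,400 / 6,300 = 85.7% of the 300 mg level. Section 9 analyses the participant at 300 mg; Section 14 drops the participant.

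**Step 3: the boundary.** At exactly 80% of the next level, Table 1 reassigns (80% or more) and its note excludes (80% or less). At 100 mg planned this is exactly 160% of plan.

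**Step 4: no window.** Assume Section 14 covers all treatment and the planned dose stays at the original Cohort level. Let f be the share of doses taken at the RDE and r the RDE divided by the original dose. Dose over plan is 1 + f(r − 1), which exceeds 1.2 when f > 0.2 / (r − 1):

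- 100 to 200 mg: f > 20%
- 200 to 300 mg or 400 to 600 mg: f > 40%
- 300 to 400 mg: f > 60%

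**Step 5: Part 1B texts side by side.** A lower dose is allowed (1.1, 4.1, 4.2). Later dosing names only the RDE (Table 2, Table 4 footnote d). The Grade 1 condition appears only in 4.1.1. One listed level below the RDE, a Day 4 move would be +33% (300 to 400 mg), +50% (200 to 300 or 400 to 600 mg) or +100% (100 to 200 mg). Section 6.6.2.1 already covers related Grade 3–4 toxicity, Grade 2–3 rash and hypersensitivity. The uncovered case is mainly a related Grade 2 non-rash AE.

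**The case against.** **Section 14 is coherent if efficacy is by planned dose.** Under the closing note of SAP Section 8.1, a participant well above plan does not represent the planned column, and dropping that person is sensible. Copying the Table 1 condition into Section 14 on its own would return over-dosed participants to their planned-dose column. This stands: planned versus actual dose must be settled first.

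**The effect is small.** Nothing is formally tested, and those dropped remain in listings and figures. Under daily dosing, 20% of 21 doses is 4.2, so passing 120% within 21 days takes at least five extra doses. This also stands. It limits the size of the problem but does not reconcile the two rules.

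**Part 1B.** The word continue suggests that Table 2 was written with Part 1B at the RDE in mind. Section 4.1.1 speaks of participants generally, two of the three dosing notes say may, and the SMC can change the dose or its meeting frequency. This reduces the point to a missing cross-reference, but a site still has no Part 1B text to go by.

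**Stronger readings that a reader might infer.**

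- *That Table 2 requires an unsafe increase.* The documents do not show that a step up is intended; the wording may simply not be aligned with the lower-dose option.
- *That a given number of the 12 participants would be affected.* The documents give no AE rate, so any count would rest on an invented one.
- *That participants moved up on Day 4 would fall out of the efficacy summaries.* In the first 21 days from Day -7 there are 13 doses (Day -7, Day 1, Days 4 to 14). Against 13 planned doses at the lower level, (2 + 11r) / 13 gives 128% to 185%. Against 21 planned daily doses, (2 + 11r) / 21 gives 79% to 114%, and the 120% rule is not reached. With the RDE as the Cohort dose, (2/r + 11) / 13 gives 92% to 96%. The SAP does not say which denominator applies in Part 1B, so this inference is not supported.

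**Conclusion.** The SAP point holds as a plain inconsistency. With the 4.1.1 dose levels, Sections 9 and 14 give opposite results above 120% of plan at 200, 300 and 400 mg and above 160% at 100 mg. Without a 300 mg level, the limit at 200 mg is also 160%. At 600 mg the Section 9 note has nothing to compare with. This follows from the text alone.

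The further risk to participants switched to the RDE under 4.1.1 depends on two assumptions: that Section 14 covers all treatment, and that the planned dose is not updated after the switch. The consequence is limited to secondary, descriptive efficacy summaries, but it decides who is counted in very small columns.

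The Part 1B point is a minor clarification. It matters only if the SMC chooses a dose below the RDE, and then mainly for a participant with a related Grade 2 non-rash AE after one of the two single doses. If Part 1B runs at the RDE, it has no effect.

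**What to change.** **SAP, before database lock.**

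1. State once that efficacy is analysed by actual dose, as Section 9 and the FAS/SAF definition already have it, and correct the closing note of Section 8.1.
2. In Section 14, replace the plain 120% rule with the condition in the Table 1 note, over the same first 21 days.
3. Change that note to below 80% of the next higher level, so that it no longer overlaps Table 1.
4. State the rule for the highest level, and name the set of levels used, including whether 300 mg belongs to it.

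The cost is a few sentences and no new data.

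**Protocol, optional but cheap.** In 4.1.2, both Table 2 notes and Table 4 footnote d, say that when Part 1B is run below the RDE, participants stay on the Part 1B dose and may move to the RDE only under the 4.1.1 condition (no treatment-emergent related AE above Grade 1), subject to 6.6.2.1. This adds no visits, since AE assessment in Table 2 is already continuous.

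The downside concerns the Day 4 biopsy. Table 2 says "The second biopsy must be collected on D4 from 2 to 4 hours after study intervention", so some of these biopsies would be taken below the RDE. Section 4.1.2 lets the Sponsor add participants if too few paired biopsies are obtained.
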